4.1. Targeted primary end point and secondary end points (effectiveness and safety parameters)

Main objective is the effect of TMS on psychomotor retardation (PR) in patients with major depressive disorder or schizophrenia. Primary outcome marker will be the change in psychomotor performance as assessed by Salpêtrière Retardation Rating Scales (SRRS). Clinical response will be defined as a 30% reduction of the SRRS baseline scores.

Secondary targets will be the effect of TMS on other motor parameters and on specific symptoms e.g. depressive or negative symptoms.

Efficacy parameters: TMS parameters may be of critical role determining the effect of the applied TMS on motor symptoms.

Safety parameters: As specific safety factors in relation to TMS, patients with 1. past history of epilepsy, or 2. other increased neuronal activity in Electroencephalography (EEG), 3. MRI contraindications and 4. substance misuse will be excluded. EEG recordings will be held for all patients before the beginning of TMS. Patients will be screened every 5 sessions with SRRS and actigraphy. In case of moderate deterioration of motor performance (30% change of initial ratings of SRRS or/and actigraphy) or adverse reactions during the TMS protocol, patients will be excluded from further participation in the study. .

4.2. Specification of the parameter that is of primary interest and other parameters that will be assessed as additional, secondary end points.

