
After collecting all data, the final analyses will follow and manuscripts will be written.

Settings

Recruitment, screening and selection of patients will take place at the University Hospital of Psychiatry in Bern. The assessments and the TMS sessions will be carried

out at the Lab of the Department of Psychiatric Neurophysiology, University Hospital of Psychiatry in Bern.

Study duration for each participant

In total the duration for each participant will be as following

Duration of assessments

A) Pre TMS clinical ratings & tests	210 min
B) TMS sessions	30 min x 15 sessions=450 min
C) Post- TMS clinical ratings & tests	210 min

Procedure of unblinding

Reassessments after TMS sessions will be carried out by a rater, blinded to the **stimulation** allocation. The data of patients such as the TMS configuration delivered will be concealed in a sealed and opaque envelope and kept by the main investigator. The envelope will be opened only in case of adverse reactions, leading to discontinuation of the **rTMS sessions** and exclusion from the study.

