7.1. Safety parameters: measuring methods and times

Specific safety parameters for TMS include: past history of epilepsy, pregnancy, other increased neuronal activity in Electroencephalography (EEG), MRI contraindications and substance misuse other than nicotine. Female patients will take a urine pregnancy test before the beginning of the TMS sessions and they will be required to use contraceptive methods during the **study** in order to enroll in the study. In case of a suspicion of a pregnancy during the **study** despite the use of contraceptives a urine test will be taken. These parameters will be observed and are explicit exclusion criteria. EEGs of all patients will be recorded before the beginning of TMS. Patients displaying abnormal EEG findings will be excluded. The rest of above mentioned parameters will be as well observed and are explicit exclusion criteria. After every 5 sessions, assessments of gross motor behaviour (SRRS,

actigraphy) will be repeated. In case of moderate deterioration of motor performance (30% change of initial ratings) patients will be excluded from the **study**.

7.2. Guarantee of follow-up examination of patients in case of adverse reactions.

The study will be carried out according to the protocol. In case of serious adverse events, which may be connected to the TMS **stimulation** or any relevant assessments (Art.42, KlinV), the Ethics Committee will be as soon as possible informed by the sponsor. Serious adverse events may include seizures or exacerbation of psychiatric symptoms. In such cases the TMS sessions will be immediately stopped and the patient will be excluded from the study. A MRI examination will be held and any necessary additional medical consultations will be arranged.

8. Statistics

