9.1. Safety precautions

The specific risks for TMS include past history of epilepsy, pregnancy, other increased neuronal activity in Electroencephalography (EEG), MRI contraindications and substance misuse other than nicotine. EEGs of all patients will be recorded before the beginning of TMS. Patients displaying abnormal EEG findings will be excluded. Female patients will take a urine pregnancy test before the beginning of the TMS sessions and they will be required to use contraceptive methods during the **study** in order to enroll in the study. In case of a suspicion of a pregnancy during the **study** despite the use of contraceptives a urine test will be taken. The rest of above mentioned parameters will be as well observed and are explicit exclusion criteria.

After every 5 sessions, assessments of gross motor behaviour (SRRS, actigraphy) will be repeated. In case of moderate deterioration of motor performance (30% change of initial ratings) during the **study**, patients will be excluded from the TMS. The investigators are responsible for the observation of the above mentioned criteria and the screening of patients. Patients will have to provide written informed consent, which will include explicit questions referring to the exclusion criteria. The safety criteria will be asked again before the beginning of TMS **sessions** and participants will have to warrant that none of the exclusion criteria is fulfilled.

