9.2. If appropriate: exit examination in case of dropout

At the end of every week of the **TMS stimulation**, assessments of gross motor behaviour (SRRS, actigraphy) will be repeated. In case of moderate deterioration of motor performance (30% change of initial ratings), patients will be excluded from the **study**. In case of seizures or persisting headaches a Magnetic Resonance Imaging Examination will be held for diagnostic purposes.

10. Duties of the investigator

10.1. Confirmation that the conduct of the study will be in accordance with the GCP protocol, the current legal regulations and rights.

Hereby investigators confirm that they have knowledge of the GCP protocol, according to which the study will be carried out. All current legal regulations and rights will be additionally taken into account.

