10.2. Adverse reactions, protocol changes, other changes, progress report and final report

Serious adverse events (SAE) may include seizures or exacerbation of psychiatric symptoms, which may be connected to the TMS or any relevant assessments (Art.42, KlinV). In such cases the TMS sessions will be immediately stopped and the patient will be excluded from the study. Hereby the investigators guarantee that in case of any adverse events, as well as protocol changes or other changes, the Ethics Committee will receive a progress report and final report. Additionally, investigators confirm the knowledge of the AKEK safety reporting procedures (Arbeitsgemeinschaft der Schweizerischen Forschungs- Ethikkomissionen für klinische Versuche).

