11.1. Potential risks/ benefits balance

Clinical ratings & questionnaires:

The clinical tests and the questionnaires are non-invasive methods, used mainly in route examinations with no reported side effects.

TMS sessions:

TMS is a well known, clinical, diagnostic and therapeutic, non-invasive tool, widely used with seldom reported adverse reactions, as supported by an extensive body of studies and meta-analyses (Padberg & George, 2009). In rare single cases, seizures and mild headaches have been reported, while in very few cases negative effects on cognition, mood and various hormone levels were elicited (Wasserman, 1998; Burt et al., 2002). The TMS-induced seizures were in most cases self-limiting, and did not seem to have permanent sequel. Once again, it is important to point out that the risk of adverse reactions is noticeably low, below 1/1000 investigations (Information Brochure on rTMS, rTMS committee of the International Federation of Clinical Neurophysiology). TMS parameters (intensity, frequency, number of stimulations) of the presented study will be in accordance to international safety guidelines (e.g. Wasserman, 1998).

TMS potential adverse effects will be minimized and the risk/benefit ratio will be supportable by following the TMS safety parameters, as they were above described. Any severe adverse effect will lead to discontinuation of the rTMS **protocol** in the respective patient. TMS exclusion criteria are past history of epilepsy, other increased neuronal activity in Electroencephalography (EEG), MRI contraindications and substance misuse. EEG recordings of all patients will be conducted before the beginning of rTMS **sessions**.

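### The rules for stopping a patient differ between sections on trigger and consequence, and section 8.5 leaves open whether a stopped patient is counted

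*Combined protocol and SAP*

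**What the plan says.** **Motor worsening.** Section 4.1 sets the trigger at a "30% change of initial ratings of SRRS or/and actigraphy" and ends participation in the study. Section 7.1 repeats the 30% rule without saying which measure must change, and concludes that "patients will be excluded from the study". Section 9.2 says "In case of moderate deterioration of motor performance (30% change of initial ratings), patients will be excluded from the" study. Section 9.1 has nearly the same sentence as 7.1, but there "patients will be excluded from the TMS".

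**Adverse events.** Section 4.1 states, with no grade, that in the case of "adverse reactions during the TMS protocol, patients will be excluded from further participation in the study". Sections 7.2 and 10.2 speak of serious adverse events: "In such cases the TMS sessions will be immediately stopped and the patient will be excluded from the study". Section 11.1 uses a third term and a narrower consequence: "Any severe adverse effect will lead to discontinuation of the rTMS" protocol, with no mention of leaving the study. Section 9.2 answers seizures or persisting headaches with an MRI and does not say whether TMS stops.

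**Unblinding.** Under section 4.3, "The envelope will be opened only in case of adverse reactions, leading to discontinuation of the" rTMS sessions and exclusion from the study.

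**Analysis.** Section 8.5 has two sentences. One admits only complete records with assessments at two time points. The next promises an intention-to-treat analysis with last observation carried forward (LOCF) for dropouts. Section 6.1 places the clinical ratings at baseline and after the last session; 4.1, 4.3, 7.1 and 9.1 add SRRS checks every five sessions. No section says whether a patient who stops early has the final assessment. Section 9.2 is headed as an exit examination but describes none beyond the weekly motor check and the MRI.

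**The concern.** Two staff members following different sections could handle the same patient differently: whether TMS stops, whether the patient leaves the study, and whether the envelope is opened. That is a problem of conduct.

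It is also a problem for the primary analysis. The primary outcome is response, defined as more than 30% improvement on the SRRS, and one reason for removal is 30% worsening on that same scale. Removal is therefore tied to the outcome. If removed patients are not counted, the rate is computed on a set from which known failures have been taken out, and the arm looks better than it was. Section 8.3 repeats the primary analysis at 25%, 50% and 75% of recruitment and allows an arm to be stopped on it, so the same distortion can enter those decisions while arms are still small.

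**Working it through.** **The sections applied to four patients**

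| Patient | Result by section |
|---|---|
| A: SRRS and actigraphy both worse by 30% after session 5 | 4.1, 7.1, 9.2: out of the study. 9.1: out of TMS only. |
| B: actigraphy alone worse by 30% | 4.1: out if either measure suffices, stays if both are needed. 7.1, 9.1, 9.2: both measures are named in the preceding sentence, but the question is left open. |
| C: mild headache | 4.1: out of the study. 7.2, 10.2, 11.1: stated threshold not met. |
| D: event both serious and severe | 4.1, 7.2, 10.2: out of the study. 11.1: rTMS stops, leaving the study not mentioned. |

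Patient A shows a direct inconsistency of consequence. C shows different thresholds, and D different consequences. B shows an ambiguity inside 4.1 that the other sections do not resolve. For C, the 4.3 envelope would be opened if 4.1 is followed, but nothing in 7.2, 10.2 or 11.1 would lead to it.

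**From the stopping rule to the analysis set**

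Take patient A, whose last SRRS is 30% worse than baseline.

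- Out of the study, complete-records sentence: no assessment after the last session, so A is not analysed. This reads the two time points as those in 6.1; if the session-5 check counted as the second one, A would stay in.
- Out of the study, ITT with LOCF: the session-5 SRRS is carried forward and A counts as a non-responder.
- Out of TMS only (9.1), final SRRS taken: A is analysed under either sentence, on the final value.

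**Size**

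The plan gives no expected number of removals, so there is no plan figure to reproduce on this point. The arm size of 20 comes from 8.2. The calculation there is consistent: w² = (0.15² + 0.15²)/0.25 = 0.18, and 79 × 0.18 = 14.22, the stated noncentrality. It is not disputed here.

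With r responders among 20 and k non-responders dropped, the analysed rate is r/(20 − k). The values r = 5 and k = 1, 3, 5 are assumptions.

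- k = 0: 5/20 = 25%
- k = 1: 5/19 = 26%
- k = 3: 5/17 = 29%
- k = 5: 5/15 = 33%

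At the first interim look (25% of 80 = 20 patients, about 5 per arm), dropping one non-responder moves 1/5 = 20% to 1/4 = 25%.

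The direction depends on who is dropped. If one of the five responders is removed, for example for a mild headache, the rate falls to 4/19 = 21%.

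**How much the either-or-both question could matter**

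Assume that each measure crosses 30% by chance with probability q at each of two interim checks (after sessions 5 and 10), independently.

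- Either measure: 1 − (1 − q)⁴. For q = 2% this is 7.8%, about 6 of 80 patients; for q = 10% it is 34.4%, about 28 of 80.
- Both measures: 1 − (1 − q²)². For q = 2% this is 0.08%, about 0 of 80; for q = 10% it is 2.0%, about 2 of 80.

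Positive correlation between the measures would narrow this gap. The values of q are not in the documents.

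**The case against.** The strongest reply is that section 8.5 already promises ITT with LOCF. Section 9.2 deals with the 30% rule under a dropout heading, which points to that sentence. A patient removed for SRRS worsening has a post-baseline SRRS from the five-session check, so LOCF would count the patient as a non-responder in the randomised arm. This stands. A reader might infer that removed patients simply vanish from the denominator; the documents support that only under the complete-records sentence. They do not say which sentence governs the primary analysis.

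Second, the adverse-event rules can all be followed at once. Sections 7.2, 10.2 and 11.1 nowhere say that lesser events are no reason to stop, and 4.1 is broad enough to contain them. This also stands: the thresholds differ, but they do not exclude one another. Yet a reader of 11.1 alone would not learn that an ungraded reaction ends participation.

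Third, *or/and* ordinarily means either or both, and the other sections name the same two measures. It is fair to call this an ambiguity within one rule and not a conflict between sections.

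Fourth, leaving the study includes leaving TMS, so 9.1 might only be incomplete. The distinction still decides whether a final SRRS is expected.

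Fifth, a reader might infer that mild headaches would remove more patients from active arms than from sham. Section 11.1 does name mild headaches, but as rare single cases, and it puts the risk of adverse reactions below 1 in 1000 investigations. No comparison of active with sham is given, so no such claim is made.

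**Conclusion.** The point holds as an inconsistency in the stopping rules with a conditional effect on the primary analysis. The consequence of the same motor worsening differs between 9.1 and 4.1, 7.1 and 9.2. The adverse-event trigger is ungraded, serious or severe depending on the section, and 11.1 stops only the stimulation. The either-or-both question in 4.1 is open.

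The response rate is biased upward if the complete-records sentence governs, the two time points are baseline and after the last session, and the patients dropped are non-responders. The third condition is met on the last available value for patients removed for SRRS worsening, but not necessarily for those removed on actigraphy alone or for an adverse reaction. Under these conditions the illustration is 25% rising to 29% for three patients dropped from an arm of 20; the counts are assumed. Under ITT with LOCF the denominator is preserved and only the value used is in question. The wording should be corrected before the plan is used; it does not show that the trial's result would be wrong.

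**What to change.** Reconcile 4.1, 7.1, 7.2, 9.1, 9.2, 10.2 and 11.1 into one rule, stated once and cross-referenced elsewhere, including from the unblinding text in 4.3. The rule should name one adverse-event grade, say whether one or both motor measures must change, and state the consequence. Which threshold is right is a clinical decision, on which no view is taken here.

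For the analysis, separate stopping TMS from leaving the study. Patients who stop TMS and still consent have the planned final SRRS and are analysed in the arm to which they were randomised. Align 8.5 with this, so that its complete-records sentence does not remove them from the primary analysis, and say which sentence of 8.5 governs it.

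The cost is protocol wording, with the notice to the Ethics Committee that 10.2 foresees for protocol changes, and one already planned assessment for each patient who stops early.

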4.4. Measures to minimize bias risk

After recruitment patients will be randomly allocated to four groups. Groups will be matched for age, gender, education and diagnose. Rater is blinded, patient is semi-blinded (has no knowledge of TMS, but could however find out where stimulation occurs).

5. Selection of the participants

5.1. Subject Recruitment

Patients with schizophrenia or major depressive disorder (MDD) according to DSM-5 criteria, displaying reduced levels of motor activity, will be recruited from the inpatient and outpatient departments of the University Hospital of Psychiatry in Bern.

5.2. Inclusion criteria

Right handed patients with MDD or schizophrenia according to DSM 5, ages 18-65 years old displaying reduced motor activity screened with the Bern Psychopathology Scale (BPS) (Strik et al., 2010). BPS is a validated, quantitative and qualitative scales for the assessment of system-specific psychotic symptoms. Diagnoses will be given through application of MINI and review of complete cases records. Patients must have normal or corrected-to-normal vision and hearing.

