displaying reduced levels of motor activity. Diagnoses will be given through application of MINI and review of the complete cases files. Only patients displaying reduced levels of motor activity assessed with Bern Psychopathology Scales (BPS) will be included and will be randomly assigned to four equal groups. Patients will be informed about the stimulation procedure and the goals of the study. Written informed consent will be obtained. Female patients will take a urine pregnancy test before the beginning of the TMS sessions and they will be required to use contraceptive methods during the TMS protocol in order to enroll in the study. In case of a suspicion of a pregnancy during the study despite the use of contraceptives a urine test will be taken. Subjects will undergo a series of diagnostic tests assessing primarily different psychomotor domains and secondarily disorder specific symptoms. Questions concerning demographic data (age, gender, education, occupational status) as well as substance use and medication will also be included. Each group will receive sessions of TMS of different stimulation parameters. Regardless of the type and the frequency of TMS, the stimulation protocol will consist of 15 daily sessions during a 3 week period. The four different stimulation conditions have been described above. Subjects will be reassessed after TMS.

Following assessments will be performed:

- Mini-International Neuropsychiatric Interview (MINI) – A validated structured diagnostic psychiatric interview.
- Bern Psychopathology Scales (BPS) – A validated quantitative and qualitative scales for the assessment of system-specific psychotic symptoms
- Actigraphy – gross motor activity levels will be recorded by wrist actigraphs
- Salpêtrière Retardation Rating Scales (SRRS) – A validated scales allowing the assessment various domains of psychomotor performance including gait, gross and facial motorics, speech and cognitive elements
- Finger tapping test – video-taped assessments of fine motor performance
- Test of Upper Limb Apraxia (TULIA) –video-taped, blinded ratings of gesture performance
- Patients with Major Depressive Disorder (MDD): Hamilton Rating Scale for Depression (HAMD), Montgomery Åsberg Depression Rating Scale (MADRS), Beck Depression Inventory (BDI) (Beck et al., 1961),

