6.1. Effectiveness parameters: measuring methods and reference dates

The efficacy of TMS sessions will be evaluated primarily as improvement in SRRS baseline score after treatment. Furthermore, we investigate the effect of TMS on gross motor behavior (SRRS, actigraphy), fine motor function (finger tapping test), and hand gesture performance (TULIA). To this purpose, clinical ratings will be assessed twice, at baseline and after the last TMS **session**. Furthermore, changes may be demonstrated by the scales assessing the disorder specific symptoms; in patients with major depressive disorder, HAMD, MADRS and BDI, in patients with schizophrenia PANSS, SANS, CAINS and the Bush Francis Catatonia Rating Scales. Statistical analysis will comprise repeated measures ANOVAs of motor variables and stimulation mode as between subject variable. Clinical response will be defined as a 30% reduction of the SRRS scores.

7. Assessment of safety

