8.1. Definition of the primary end point and secondary end points

Primary outcome of the study will be clinical response as defined by >30% improvement from the baseline score of the Salpêtrière Retardation Rating Scales (SRRS). Moreover, gross motor behavior (actigraphy), fine motor function (finger tapping test), and hand gesture performance (TULIA) will be assessed at baseline and after the last TMS. Furthermore, we will investigate the efficacy of TMS on disorder specific symptoms; in patients with major depressive disorder, HAMD, MADRS and BDI, in patients with schizophrenia PANSS, SANS, CAINS and the Bush Francis Catatonia Rating Scales will be carried out before and after TMS. Statistical analysis will comprise ANOVAs of motor variables and stimulation mode as between subject variable. Clinical response will be defined as a 30% reduction of the SRRS scores. Frequency of response will be compared between groups using Chi²-Tests.

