8.4. Planned significance level

Planned level of significance will be held as p<0.05.

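### The primary response test ignores baseline SRRS, although entry sets no SRRS level and the chance of passing the 30% mark through rating noise depends on it

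*Combined protocol and SAP*

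**What the plan says.** **Selection.** The inclusion criteria (5.2) take patients "displaying reduced motor activity screened with the Bern Psychopathology Scale (BPS"). The study design text in 4.3 repeats this: "Only patients displaying reduced levels of motor activity assessed with Bern Psychopathology Scales (BPS) will be included". Sections 5.2 and 5.3 give neither a BPS cut-off nor a minimum SRRS.

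**Outcome scale.** The list of assessments in 4.3 describes the SRRS as covering "gait, gross and facial motorics, speech and cognitive elements". It therefore reaches beyond motor activity. Section 6.1 says that "clinical ratings will be assessed twice, at baseline and after the last TMS" session, so response rests on two single ratings.

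**Primary endpoint and test.** Section 8.1 states: "Primary outcome of the study will be clinical response as defined by >30% improvement from the baseline score" of the SRRS, and "Frequency of response will be compared between groups using Chi²-Tests". Section 8.4 sets the level: "Planned level of significance will be held as p<0.05".

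**What touches baseline.** Section 4.4 names age, gender, education and diagnosis as matching factors, but not SRRS. Section 8.3 brings unequally distributed descriptive parameters in as covariates, but only in the repeated-measures ANCOVA, not in the chi-square. Section 4.1 calls the change in SRRS the primary outcome marker.

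**The concern.** A percentage of the patient's own baseline is a small number of points when the baseline is low. At a baseline of 5, more than 30% means a fall of 2 points; at 20 it means a fall of 7. With no SRRS condition at entry, patients from both ends of the scale can be randomised, and the same response label then carries different amounts of rating noise. At a baseline of 0 the percentage is undefined, and the plan does not say how such a patient is counted.

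The test that decides the trial uses none of this. Patients who respond through noise appear in every arm and pull the response rates together. With 20 per arm, one arm can also hold more low-baseline patients by chance, and the chi-square cannot correct for that although the baseline rating is already collected.

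**Working it through.** **1. The plan's own figure.** Section 8.2 compares shares of responders of 25/25/40/10% with 25% each:

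w² = Σ(p₁ − p₀)²/p₀ = (0.15² + 0.15²)/0.25 = 0.18, so w = 0.424.

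With N = 79, λ = 79 × 0.18 = 14.22. At df 3, α = 0.05 and critical value 7.81, power is 0.901. The stated 79 reproduces, so this point does not concern the sample-size arithmetic.

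**2. Response through noise alone.** Assume no true change, independent rating errors with SD e at each visit, and whole-point changes. The change then has SD √2·e. The smallest whole-point fall k that exceeds 30% of baseline B is reached with probability P(Z > (k − 0.5)/(√2·e)). With e = 2, √2·e = 2.83. The value of e is an assumption, so the last column shows the range for e = 1 to 3.

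| Baseline B | Fall needed k | (k − 0.5)/2.83 | Chance, e = 2 | Range, e = 1 to 3 |
|---|---|---|---|---|
| 5 | 2 | 0.53 | 30% | 14–36% |
| 10 | 4 | 1.24 | 11% | 1–20% |
| 15 | 5 | 1.59 | 6% | 0–14% |
| 20 | 7 | 2.30 | 1% | 0–6% |

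Without rounding to whole points, the formula is Φ(−0.3B/(√2·e)). It gives 34% when B is twice the error SD, 14% at five times and 1.7% at ten times. This treats the baseline as fixed. Simulating the ratio with error in both ratings gives somewhat lower values at moderate baselines (11% instead of 14% at five times).

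**3. What this could do to power.** Section 8.2 gives shares of responders, not response rates, so rates must be assumed. Rates of 50/50/80/20% keep the plan's proportions and its w: mean 0.50, and w² = [(0.3² + 0.3²)/4]/(0.5 × 0.5) = 0.18. Simulated power of the 4×2 chi-square at 20 per arm is then 0.94.

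Let a share s of patients have a low baseline, each with noise-response probability f. False responders change a rate r to r + (1 − r)·s·f, which shrinks every difference between arms by the factor 1 − s·f. For s = 25% and f = 35%, the factor is 1 − 0.0875 = 0.9125, and the widest gap falls from 0.60 to 0.548.

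| s | f | Power, false responders only (N for 90%) | Power, noise also hides true responses (N for 90%) |
|---|---|---|---|
| 0 | – | 0.94 (79) | 0.94 (79) |
| 25% | 15% | 0.92 (85) | 0.89 (93) |
| 25% | 35% | 0.88 (94) | 0.78 (116) |
| 50% | 15% | 0.89 (92) | 0.81 (109) |
| 50% | 35% | 0.80 (113) | 0.53 (187) |

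Nothing in the documents says which row applies, or whether s is near 0.

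**4. What the covariate buys.** In simulations with assumed SRRS means of 10 to 20 and error SD of 2 to 3, logistic regression on arm and baseline SRRS gained 2 to 3 percentage points of power over the chi-square. Part of that came from slight small-sample type I inflation of the likelihood-ratio test.

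**The case against.** The strongest reply is that the size is unknown and may be negligible. The protocol describes its patients as having psychomotor retardation, and the BPS and SRRS both rate motor behaviour, so most entrants may score well above the range where noise matters. At a baseline of 20 the noise rate is only about 1%. A baseline of 0 is an edge case that nothing in the text suggests is common. This stands as a limit on size. It is not a floor, and the plan cites no SRRS data to show that low scores will be rare.

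Second, the continuous SRRS is already analysed: 4.1 names its change as the primary outcome marker, and 8.3 plans repeated-measures ANOVA with covariates. That helps interpretation, but section 8 makes response the primary outcome, and its test stays unadjusted.

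Third, selecting on a scale other than the outcome is defensible. A minimum SRRS would select on the same noisy rating that serves as baseline, inviting regression to the mean and upward scoring at entry. In simulations with a floor of 10 and error SD 2, overall false response fell from 6.6% to 4.4% while 19% of patients were excluded (assumed true mean 15, SD 6), and from 14% to 9% with 46% excluded (mean 10, SD 5). For a single site with 24 months to treat 80 patients, that is a real price. This objection stands, and the floor is not part of the recommendation.

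A reader might also infer that the noise biases the comparison or produces false positives. The documents do not support that: 4.4 provides random allocation and a blinded rater, so the noise should be the same in every arm.

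**Conclusion.** The gap is real but modest. The chance of response through noise depends on baseline SRRS, entry does not restrict baseline SRRS, and the primary test does not use it. The consequences are a possible loss of power and no correction for chance imbalance at 20 per arm.

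The figures of about 30% at a baseline of 5 and 1% at 20 rest on an assumed error SD of 2 points. The power figures rest on assumed response rates, an assumed share of low baselines and an assumed noise probability. It would be tempting to conclude that the trial is materially underpowered for this reason, or that a minimum SRRS is required. Neither follows, because the documents give no SRRS range, rating error or baseline distribution. What can be said is that the plan leaves out of its primary test a baseline measurement that it already collects.

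**What to change.** **Change in 8.3:**

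- Pre-specify the primary comparison of response as a logistic regression with treatment arm (3-df test) and baseline SRRS as covariate. Use a penalised likelihood or an exact fallback if an arm has very few responders. This matters most at the planned looks at 25%, 50% and 75% of recruitment, which repeat the primary analysis with about 5, 10 and 15 patients per arm (for example 80 × 0.25/4 = 5).
- Keep the unadjusted chi-square as supportive, since 8.2 is powered on it.
- State how a patient with a baseline SRRS of 0 is classified.
- Report a baseline-adjusted ANCOVA of post-treatment SRRS alongside. It fits the outcome marker named in 4.1 and does not depend on the 30% cut.

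**Cost:** No new data are needed. The odds ratio becomes conditional on baseline, the gain in power is small, and the likelihood-ratio test can be slightly liberal at this sample size. The covariate addresses imbalance; it does not reclassify patients who crossed 30% through noise.

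**Left to the sponsor:** Whether to set a minimum baseline SRRS is a separate choice, to be weighed against recruitment and regression to the mean.
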